STUDY DESIGN	
This is a phase II, multicenter, open-label, study of single-agent PM060184 to evaluate efficacy in patients with advanced CRC progressing after standard therapy.
 
Initially, 24 patients who are evaluable for the primary endpoint will be included and a futility analysis will be performed (first

	
stage). If at least seven of these patients achieve PFS3, then the study will proceed to a second stage and 36 additional patients will be recruited.
 
If at least 25 of 60 evaluable patients are alive and free of progression at 12 weeks, PM060184 will be considered active and deserving potential development in this setting.

SUBSTUDY DESIGN	
An exploratory substudy will address pharmacogenomic and pharmacogenetic objectives. All patients who participate in the PM60184-B-002-17 clinical trial will be eligible for the substudy if they voluntarily sign a separate informed consent. Refusal to participate in the substudy will not affect a patient's participation in the clinical trial.

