	
modeling and/or non-compartmental analysis.
 
 • Metabolomics of PM060184, i.e., intra- and interpatient systemic variations in the patient’s pre- and post-treatment metabolic profile. • PGt of PM060184 will be evaluated to identify the presence or absence of germline mutations or polymorphisms that may help explain individual variability in the main PK parameters and safety outcomes. • PGx of PM060184 will be evaluated to determine predictive/prognostic markers of response and/or resistance to PM060184. 
Methods of analysis:
 
Frequency tables will be prepared for categorical variables and summary tables, including median, mean, standard deviation, minimum, and maximum values for each variable, will be used for continuous variables. Exploratory comparisons will be performed at a 0.05 level.
 
The exact binomial estimator and its 95% confidence interval (CI) will be used for the primary endpoint (PFS3) and categorical variables (i.e., ORR).
 
Time-to-event variables (DOR, PFS, OS) and their fixed time estimates will be analyzed according to the Kaplan-Meier method.
 
Safety analyses will consider AEs, SAEs, analytical results, deaths and the reasons for study discontinuations. All AEs and SAEs will be graded according to the NCI-CTCAE v.4, and will be coded using MedDRA.
 
PRO analysis will be performed on summary measures and longitudinal modelling of patients’ QLQ responses.
 
Other analyses will include: number of prior treatment lines, prior oxaliplatin exposure, KRAS status, BRAF-like expression, and other prognostic/predictive factors.

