9.3 SAMPLE SIZE

Patients will be treated with PM060184 to test the null hypothesis (H0) that 30% or less patients are alive and free of progression at twelve weeks (PFS3) according to RECIST v.1.1 ($p \leq 0.30$) versus the alternative hypothesis (H1) that 50% or more patients are alive and free of progression at 12 weeks according to the aforementioned criteria ($p \geq 0.50$). The variance of the standardized test is based on the null hypothesis. The type I error (alpha) associated with this one-sided test is 0.025 and the type II error (beta) is 0.1; hence, statistical power is 90%.

Sixty evaluable patients are necessary to test the hypothesis. A futility analysis using O'Brien-Fleming boundaries is planned when 24 patients can be evaluated (first stage). If there are seven or more patients achieving PFS3 in the first stage then the trial will proceed to a second stage and a total of 60 patients will be recruited.

If at least 25 of 60 evaluable patients are alive and free of progression at 12 weeks then the null hypothesis can be rejected and PM060184 considered active and deserving potential development in this setting.

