6.2. Efficacy Analysis Methods

6.2.1. Primary Endpoint

For the evaluation of the primary endpoint (PFS3), the efficacy population and the exact binomial estimator (count and percentage) including its 95% confidence interval will be used.

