11.3.1. Primary Analysis

Patients who are evaluable for efficacy but have not been followed-up for at least 12 weeks (+/- 5 days) will be categorized as PFS3=No.

Table 11.3.1 PFS3 rate (binomial exact estimator and 95% confidence interval).

	Proportion	Lower 95% limit	Upper 95% limit
PFS3*			

(*) Progression-free-survival rate at 12 weeks (+/- 5 days).
Binomial exact estimator and 95% CI.

Listing 11.3.2 Censored patients.

Patient	PFS3 rate	PFS (months)	Reason for censoring

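### The planned PFS3 rate and its one-sample exact 95% CI ignore the futility stop at 24 patients; a two-stage interval and a supplementary adjusted estimate would be a cheap improvement

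*Protocol*

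**What the plan says.** The design has two stages. Protocol Synopsis (Study Design): "If at least seven of these patients achieve PFS3, then the study will proceed to a second stage". The second stage adds 36 patients, for 60 in total. Protocol 8.1 and 9.3 and SAP 5.2 and 8.14 give the same rule, so six or fewer of 24 ends the trial.

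The primary analysis is a single-sample one. The sentence "The exact binomial estimator and its 95% confidence interval (CI) will be used for the primary endpoint (PFS3") stands in the Synopsis and in protocol 9.5. SAP 6.2.1 says that "the exact binomial estimator (count and percentage) including its 95% confidence interval will be used", and SAP Table 11.3.1 is titled "PFS3 rate (binomial exact estimator and 95% confidence interval"). SAP section 6 pools the two stages for the main efficacy results.

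Neither document gives a stage-adjusted estimate or interval, or mentions what the futility stop does to estimation. SAP 8.14 covers only the decision to continue.

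**The concern.** When the sample size depends on the first-stage count, count/n is no longer unbiased and a one-sample Clopper-Pearson interval no longer has a guaranteed level. Trials that start badly are frozen at 24 patients with a low rate and get no second stage to pull them back. Trials that continue have been selected for a good start.

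PFS3 is the only primary endpoint, and a positive result is meant to support further development. The reported rate and interval are therefore likely to be carried forward, and an interval labelled exact will be read as one that holds its level.

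**Working it through.** **Inputs (protocol 9.3).** The "null hypothesis (H0) that 30% or less patients are alive and free of progression at twelve weeks (PFS3"); the "alternative hypothesis (H1) that 50% or more patients are alive and free of progression at 12 weeks". "The type I error (alpha) associated with this one-sided test is 0.025" and "the type II error (beta) is 0.1; hence, statistical power is 90"%. Stage 1 has 24 patients, continuation needs at least 7, the total is 60, and success needs at least 25.

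**The plan's own figures reproduce.** n = [1.960·√(0.30·0.70) + 1.2816·√(0.50·0.50)]² / 0.20² = (0.898 + 0.641)² / 0.04 = 59.2, so 60. Critical count = 60·0.30 + 1.960·√(60·0.21) = 18 + 6.96 = 24.96, so 25.

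**Bias of count/n.** Let X1 ~ Bin(24, p) and X2 ~ Bin(36, p). The estimate is X1/24 if X1 ≤ 6 and (X1+X2)/60 otherwise. Full enumeration gives:

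| True rate | P(stop at 24) | Mean of count/n | Bias, all outcomes (points) | Bias given continuation (points) |
|---|---|---|---|---|
| 30% | 38.9% | 27.8% | −2.2 | +2.4 |
| 35% | 21.1% | 33.3% | −1.7 | +1.4 |
| 40% | 9.6% | 39.0% | −1.0 | +0.7 |
| 50% | 1.1% | 49.8% | −0.2 | +0.1 |

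Check at 30%: stopped trials average 20.75% (9.25 points low) and continued trials 32.35%. So 0.389·20.75 + 0.611·32.35 = 8.07 + 19.77 = 27.8%. The largest overall bias is −2.21 points, at a true 28%.

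**Coverage of the one-sample exact CI under the two-stage design.** I summed the probability of every outcome whose interval contains p, for p from 0.05 to 0.80 in steps of 0.0005. The minimum is 94.3%, at p = 0.4675. Coverage is slightly below 95% at 0.379–0.3835, 0.422–0.432, 0.4675–0.482 and 0.4845–0.4855.

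The cause is visible at 0.4675. The upper limit for 6/24 is 46.71% and for 20/60 is 46.69%, so every stage-1 stop and every 60-patient result of 20 or fewer misses low, with total probability 4.26%. Results of 37/60 or more miss high, with probability 1.44%. Coverage is 100 − 4.26 − 1.44 = 94.3%.

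**Two-stage exact CI.** Order the outcomes 0/24 to 6/24, then 7/60 to 60/60. The lower limit solves P(this outcome or higher) = 0.025; the upper limit solves P(this outcome or lower) = 0.025. On the same grid its minimum coverage is 95.1%.

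**UMVUE.** For a 60-patient result x, UMVUE(x) = Σ C(23, x1−1)·C(36, x−x1) / Σ C(24, x1)·C(36, x−x1), summed over x1 ≥ 7. For a stopped trial it equals X1/24. Its enumerated bias over all outcomes is zero at every rate checked.

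| Result | count/n | One-sample CI | Two-stage CI | UMVUE |
|---|---|---|---|---|
| 18/60 | 30.0% | 18.8–43.2% | 19.5–47.2% | 34.2% |
| 20/60 | 33.3% | 21.7–46.7% | 22.1–48.6% | 36.0% |
| 25/60 | 41.7% | 29.1–55.1% | 29.1–55.3% | 42.2% |
| 30/60 | 50.0% | 36.8–63.2% | 36.8–63.2% | 50.0% |

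**Limits of the UMVUE.** Given continuation, its upward bias is +5.9 points at 30%, +3.5 at 35% and +1.9 at 40%, about 2.5 times that of count/n. Root mean squared error, count/n against UMVUE, is 7.1 v 8.3 points at a true 25%, 7.9 v 8.3 at 30%, 8.2 v 7.9 at 35% and 8.0 v 7.5 at 40%.

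**The case against.** The plan is explicit and consistent on this point. PFS3 is defined as a percentage of patients, and count/n reports that directly. Both decision rules work on counts. The adjustment exceeds 2 points only at about 20/60 or fewer, results that already fail the 25/60 rule; at 25/60 the rate moves by 0.5 points. The overall downward bias comes from stopped trials, whose estimate the UMVUE leaves unchanged. All of this stands, and it is why the point is a small one.

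Three stronger readings are tempting and should be resisted.

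- A reader might infer that the UMVUE should replace count/n as the headline. That is a trade-off, not a correction. Development is considered only after continuation to 60, and there the UMVUE is the more optimistic number. It also has the larger mean squared error at the true rates of 30% and 25% that were checked.
- A reader might infer that the bias puts the go/no-go decision in doubt. It does not, because no estimate enters either rule. The 30% null also lies inside both intervals at 25/60 (lower limit 29.1% either way), but that comes from setting the boundary by normal approximation and is a separate matter from the futility stop.
- In the other direction, a reader might assume that a Clopper-Pearson interval must still cover at least 95%. That guarantee is for a fixed sample size and fails here, though by less than one point.

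**Conclusion.** The point holds as a cheap improvement. Count/n is biased downward over all outcomes by up to about 2.2 points, and upward by a similar amount near the null among trials that reach 60. At the 50% alternative both biases are 0.2 points or less. The one-sample exact interval can fall to 94.3% coverage for true rates between the null and the alternative. The two-stage interval stays above 95% on the grid examined and is barely different at 25/60 and above.

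These figures assume that the futility rule is enforced as written and that exactly 24 or 60 evaluable patients are analysed. If the trial continued regardless of the first-stage count, the bias would disappear.

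**What to change.** In protocol 9.5, SAP 6.2.1 and SAP Table 11.3.1:

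1. Keep count/n as the main reported PFS3 rate, and say that under the futility stop it is biased downward over all outcomes and upward given continuation.
2. Replace its interval, or accompany it, with a two-stage exact 95% CI that orders all first-stage stops below all 60-patient results.
3. Add the UMVUE for the 24/60 design as a prespecified, labelled supplementary row. State that it is unbiased only over all outcomes, exceeds count/n in trials that continue (visibly so at low counts), and has larger mean squared error at true rates of 30% or less.

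This should be fixed before results are seen, since choosing an estimator afterwards would be open to criticism. It needs no new data, patients or change of decision rule. The cost is a few lines of code, one or two table rows, and a supplementary rate that differs from count/60 and needs a footnote.

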*** Permitted windows for assessments before Day 1 of Cycle 1:**

If physical examination, ECOG PS, vital signs, hematology/biochemistry were assessed >10 days before Day 1 of Cycle 1, the tests must be repeated within 2 days before the first study drug administration.

If pregnancy test was done >7 days before Day 1 of Cycle 1, the test must be repeated within 2 days before the first study drug administration.

If tumor assessments were done >28 days before Day 1 of Cycle 1, the tests must be repeated within 2 days before the first study drug administration.

A patient should only be treated if eligibility criteria are still met according to assessments performed closest to treatment start.

Permitted windows for assessments after Day 1 of Cycle 1:

- 2 days for physical examination and ECOG PS (on Day 1) and for vital signs (on Days 1 and 8), always before study drug administration.

+ 7 days for tumor assessments (except in Week 12 when there is a maximum 5-day window).

± 2 days for Day 1 study drug administration (from Cycle 2 onwards).

± 2 days for Day 8 study drug administration.

- 2 days for laboratory tests. To confirm criteria for treatment continuation, laboratory assessments must be performed within 2 days prior to drug administration.

If a drug administration is delayed beyond the permitted protocol window, assessments planned for the original administration day must be repeated on the day the dose is finally administered.

1. EOT assessments should take place approximately 30 days (\pm 15 days) after the last drug administration or before starting new therapy. Loss to follow-up, or failure to attend the EOT visit due to a deteriorated clinical condition or due to personal reasons such as returning to their previous hospital, will not be considered protocol deviations.

8. The plasma PK of PM060184 will be evaluated in Cycle 1 and Cycle 2 during both stages of the study. Ten plasma PK samples are required from patients included in the first stage: just before start of administration, just before EOI, and then 15 min, 30 min, 1 h, 2 h, 4 h, 6 h, and 12.5 h (Day 1) and 24.5 h (Day 2) after EOI in Cycle 1 and Cycle 2. Only eight plasma samples are required from patients included in the second stage: the samples scheduled at 12.5 h and 24.5 h after EOI in Cycle 1 and Cycle 2 are not required.
9. One blood sample should be collected prior to each drug administration on Day 1 and Day 8 of Cycle 1, and also on Day 8 of Cycle 2.
10. If the patient consents to the substudy, an additional blood sample for PGt analysis should be collected at any time during the trial but ideally at the same time as the pretreatment PK sample (sample #1) of Cycle 1.
11. If the patient consents to the substudy, the availability of tumor tissue samples used for the initial diagnosis of the disease, or obtained at relapse, should be confirmed and should be prepared and shipped during the trial following the instructions detailed in a separate laboratory manual.
12. To be performed every six weeks (+ 7 days, except for Week 12 when a window of \pm 5 days applies). **The Week-12 disease evaluation is the primary endpoint of the study and should be performed in all non-PD patients (including those who discontinued treatment without progression).** The same radiological method should be used throughout the study for each individual patient. Anonymized copies of images showing a response (CR or PR) must be submitted to the Sponsor. Tumor assessment should be performed about every three months during follow-up in patients who discontinue treatment without disease progression. **Note: patients without disease progression who discontinue treatment due to a drug-related AE must be followed both for the AE AND for efficacy (see 2. above).**
13. Baseline conditions, signs and symptoms and ongoing toxicities at registration should be reported as screening AEs. Clinical assessment of the patient's signs and symptoms (if any and including nurses' assessment and patient-reported issues) should continue on an ongoing basis throughout the study and be reported at least every cycle as AEs graded according to NCI-CTCAE v.4. SAEs will be collected from the time of IC signature (reported in paper if a patient is not yet registered). During screening and pretreatment periods, AEs are considered baseline and non-treatment emergent. If a condition previously reported in Medical History changes during treatment, the event should be reported as an AE.
14. Patients will be asked to complete both QLQs at baseline, on Day 8 of each cycle, at the end-of-treatment visit. Patients will be asked to complete the QLQ-CIPN20 (only) during the follow-up period (every three months until start of subsequent antitumor therapy). If a patient discontinues treatment due to grade \geq 3 PN, however, the QLQ-CIPN20 should be completed more frequently during the follow-up period (every month after EOT) until recovery to grade \leq 2 (or until start of subsequent antitumor therapy).

Assessment details

Biochemistry-A: ALP, AST, ALT, total bilirubin (and direct bilirubin if total is $>1.5 \times$ ULN), GGT, creatinine/CrCL (Cockcroft-Gault formula), glucose, LDH, and serum electrolytes (Na^+ , K^+ , Total calcium).

Biochemistry-B: Total proteins and albumin.

ECG: including rhythm definition and PR interval; heart rate; QT interval (raw); QRS complex duration, as well as

any ECG anomaly or variation (change in grade) with respect to baseline.

Hematology: Complete blood count, differential WBC (neutrophils, lymphocytes), hemoglobin, and platelets.

Left ventricular ejection fraction: assessed by ECHO or MUGA scan.

Physical examination: Including weight, height (when needed for BSA calculation) and clinical assessment. BSA and dosing should be recalculated in the event of weight variation of $\pm 10\%$.

Tumor assessment: Clinical and radiological disease assessment using RECIST v.1.1. Helical i.v. and oral contrast-enhanced CT-scan (if appropriate) for chest, abdomen and pelvis and other areas of suspected diseases. If i.v. contrast is contraindicated for the CT-scan, chest evaluation should be performed using non-contrast CT and abdomen/pelvis evaluation using gadolinium-enhanced MRI. Tumor markers alone or chest radiography alone are not sufficient to assess tumor burden.

Vital signs: Heart rate, arterial blood pressure, and temperature

Abbreviations

AE, adverse event; ALP, alkaline phosphatase; ALT, alanine aminotransferase; AST, aspartate aminotransferase; β -hCG, beta subunit of human chorionic gonadotropin; BSA, body surface area; CIPN, chemotherapy-induced peripheral neuropathy; CR, complete response; CrCL, calculated creatinine clearance; CT, computed tomography; ECG, electrocardiogram; ECHO, echocardiography; ECOG, Eastern Cooperative Oncology Group; EOI, end of infusion; EOT, end of treatment; GGT, gamma-glutamyltransferase; IC, Informed Consent; i.v., intravenous; LDH, lactate dehydrogenase; LVEF, left ventricular ejection fraction; MRI, magnetic resonance imaging; MUGA, multiple-gated acquisition; NCI-CTCAE, National Cancer Institute Common Terminology Criteria for Adverse Events; PD, progressive disease; PGt, pharmacogenetics; PK, pharmacokinetics; PN, peripheral neuropathy; PR, partial response; PRO, patient reported outcomes; PS, performance status; QLQ, quality of life questionnaire; RECIST, Response Evaluation Criteria in Solid Tumors; SAE, serious adverse event; ULN, upper limit of normal; WBC, white blood cells; WOCBP, woman of childbearing potential.

LIST OF ABBREVIATIONS AND DEFINITIONS OF TERMS

5-HT₃	Serotonin
5-FU	5-fluorouracil
ABP	Arterial Blood Pressure
AE	Adverse Event
ALP	Alkaline Phosphatase
ALT	Alanine Aminotransferase
ANC	Absolute Neutrophil Count
ANOVA	Analysis of Variance
ASCO	American Society of Clinical Oncology
AST	Aspartate Aminotransferase
BSA	Body Surface Area
BSC	Best Supportive Care
CI	Confidence Interval
CIPN	Chemotherapy-induced Peripheral Neuropathy
CL	Clearance
CR	Complete Response
CRC	Colorectal Cancer
CrCL	Creatinine Clearance
CT	Computed Tomography
d	Day
DLT	Dose-limiting Toxicity
DNA	Deoxyribonucleic Acid
DP	Drug Product
DOR	Duration of Response
DS	Drug Substance; Degree of Substitution
ECG	Electrocardiogram
ECHO	Echocardiography
ECOG	Eastern Cooperative Oncology Group
e-CRF	Electronic Case Report Form
EGFR	Epidermal Growth Factor Receptor
EOI	End of Infusion
EORTC	European Organisation for the Research and Treatment of Cancer
EOT	End of Treatment
FP	Fluoropyrimidine
G-CSF	Granulocyte Colony-stimulating Factor
GCP	Good Clinical Practice
GGT	Gamma-glutamyltransferase
GI₅₀	Growth Inhibition at 50%
GMT	Greenwich Meridian Time
HCG	Human Chorionic Gonadotropin
HIV	Human Immunodeficiency Virus
HR	Heart Rate
HSD	Honestly Significant Difference
IB	Investigator's Brochure
IC	Informed Consent
ICF	Informed Consent Form
ICH	International Conference on Harmonization
IEC	Investigational Ethics Committee
IF	Immunofixation
IHC	Immunohistochemistry
IMP	Investigational Medicinal Product
IRB	Institutional Review Board
i.v.	Intravenous(ly)

LC-MS/MS	Liquid Chromatography/Mass Spectrometry/Mass Spectrometry
LDH	Lactate Dehydrogenase
LVEF	Left Ventricular Ejection Fraction
mCRC	Metastatic Colorectal Cancer
MedDRA	Medical Dictionary for Regulatory Activities
min	Minute
MRI	Magnetic Resonance Imaging
mRNA	Messenger Ribonucleic Acid
MTD	Maximum Tolerated Dose
MTI	Microtubule Inhibitor
MUGA	Multiple-gated Acquisition Scan
NCI	National Cancer Institute
NCI-CTCAE	National Cancer Institute Common Terminology Criteria for Adverse Events
NSCLC	Non-small Cell Lung Cancer
OPLS	Orthogonal Partial Least-squares to Latent Structures
ORR	Overall Response Rate
OS	Overall Survival
PCA	Principal Component Analysis
PCR	Polymerase Chain Reaction
PD	Progressive Disease
PFS	Progression-free Survival
PFS3	Progression-free Survival at 12 weeks (three months)
PGt	Pharmacogenetics
PGx	Pharmacogenomics
PhV	Pharmacovigilance
PIF	Peak Inspiratory Flow
PK	Pharmacokinetics
PN	Peripheral Neuropathy
PR	Partial Response
PRO	Patient Reported Outcomes
PS	Performance Status
PSN	Peripheral Sensory Neuropathy
QoL	Quality of Life
QLQ	Quality of Life Questionnaire
q28d	Every 28 Days
q3wk	Every Three Weeks
q4wk	Every Four Weeks
RD	Recommended Dose
RECIST	Response Evaluation Criteria in Solid Tumors
RNA	Ribonucleic Acid
RR	Respiratory Rate
Rt-m/z	Retention Time and Mass-to-charge Ratio Pairs
RT-PCR	Reverse Transcription Polymerase Chain Reaction
SAE	Serious Adverse Event
SD	Stable Disease
ULN	Upper Limit of Normal
UPLC	Ultra Performance Liquid Chromatography
U.S.	United States of America
V₂	Peripheral Volume
V_{ss}	Volume of Distribution at Steady State
VEGF	Vascular Endothelial Growth Factor
WBC	White Blood Cells
WHO	World Health Organization

WMA
WOCBP

World Medical Association
Women of Childbearing Potential

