6.3.4 Replacement of Patients

Patients must be replaced if they are considered not evaluable for efficacy for the primary endpoint (PFS3), i.e., if they are withdrawn from the study due to significant clinical deterioration of unknown reason, hypersensitivity reactions, unrelated AEs without any tumor assessments after the start of study treatment, if they receive less than one complete treatment cycle (at least two PM060184 dose administrations over two cycles unless treatment discontinuation was due to unmanageable toxicity), or do not have the disease assessment at Week 12 (except in the case of treatment discontinuation/death due to a treatment-related AE, symptomatic deterioration due to the disease, clinical progression, PD or death due to malignant disease).

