8. STUDY EVALUATIONS

8.1 EFFICACY

Patients will be evaluable for efficacy if they receive at least one complete treatment cycle (or two PM060184 dose administrations over two cycles) and have, at least, one disease assessment at Week 6 and another one at Week 12.

In addition, any patient who presents disease progression, symptomatic deterioration due to the disease or clinical progression, dies due to malignant disease, discontinues treatment due to unmanageable toxicity, or dies or discontinues treatment due to a treatment-related AE before evaluation of the response at Week 12 will also be considered evaluable for the primary endpoint and classified as a non-responder.

Patients who have no disease assessment at Week 6 but remain on treatment and are assessed at Week 12 (or later, and with no evidence of disease progression) will be considered evaluable for efficacy.

Patients who refuse further treatment before Week 12 due to reasons other than related AEs not considered unmanageable toxicity will be replaced.

A futility analysis will be performed once the first 24 evaluable patients complete the Week 12 (\pm 5 days) tumor assessment; progress; die due to PD; or discontinue treatment due to unmanageable toxicity (whichever occurs first). If seven patients or more achieve PFS3, then 36 additional patients will be recruited (second stage).

Tumor assessment will be measured using RECIST v.1.1 ([17](#)).

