6.1. Planned Analyses and Definitions

Primary endpoint

Progression-free survival rate at 12 weeks, defined as the rate estimate of the percentage of patients who are alive and progression-free at 12 weeks (~3 months) after the first treatment administration.

Secondary endpoints

The following time-related parameters will be analyzed according to available follow-up data:

- ***Overall Survival***, defined as the time from the first day of treatment to the date of death or last contact.
- ***Progression-free Survival***, defined as the time from the first day of study treatment to the day of assessment of progression, death or last tumor evaluation.
- ***Overall Response Rate***, defined as the percentage of patients with objective response (OR), either complete response or partial response according to the RECIST v.1.1.
- ***Duration of Response***, defined as the time between the date when response criteria (PR or CR, the first to be reached) are fulfilled and the first date when PD, recurrence or death is objectively documented.
- ***Profiles of peripheral neuropathy and quality of life*** as reported by patients using the EORTC QLQ-CIPN20 and QLQ-C30.

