6.2.2. Secondary Endpoints

Time-to-event variables (DOR, PFS and OS) and their fixed time estimates will be analyzed according to the Kaplan-Meier method. Kaplan-Meier curves will be plotted.

For categorical variables, comparisons will be carried out by a Fisher exact test and a multivariate analysis by logistic regression. For time-to-event variables, comparisons will be carried out by a log-rank test and by a Cox regression analysis. No formal conclusions will be expected on these grounds. Exploratory comparisons will be performed at a 0.05 level.

If appropriate, exploratory multivariate models (main effects or including interaction terms) will include all prognostic factors/covariates widely reported and recognized by oncologists: age, age at diagnosis, baseline ECOG PS (Eastern Cooperative Oncology Group Performance Status), stage at diagnosis, Tumor primary location: right vs left side tumors; sites of metastasis; visceral vs non visceral, body mass index (BMI), body surface area (BSA), time from diagnosis to first infusion, time from diagnostic of metastatic disease to first infusion, prior advanced treatment lines, last prior therapy PFS, prior oxaliplatin exposure, KRAS status, BRAF-like expression, any relevant concomitant medication at baseline; EORTC-QLQ-C30 and QLQ-CPN20 score at baseline and other prognostic/predictive factors determined by the oncologist. The total number of variables included in the final model will always be in accordance with the number of events and the sample size, thus, whenever possible, no more than one variable per ten events will be included. The parameter estimates, hazard ratios and p-values of the variables retained in the model will be presented.

A sensitivity analysis for PFS including all treated patients will be performed. Event will be defined as progression or death irrespective of the subsequent therapies received for this analysis.

Waterfall plots will be used to describe the best variation of the sum of target lesions during treatment. Questionnaires scores over time will be described by time series charts, if appropriate.

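### As written, some patients who stop PM060184 early and start another antitumor therapy before Week 12 can still count as PFS3 successes or be replaced

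*Protocol*

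**What the plan says.** **Endpoint.** Protocol 9.1 and SAP 3.3 and 6.1 require only that the patient be alive without progression 12 weeks after the first dose. None of them mentions other anticancer treatment.

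**Scan.** Footnote 12 of the Schedule of Assessments and Procedures says the Week-12 evaluation "should be performed in all non-PD patients (including those who discontinued treatment without progression". It sets no cut-off at new therapy. It mandates the scan but does not score it.

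**Scoring.** Under Protocol 8.1 and SAP 4, a patient with the minimum dosing is evaluable if they "have, at least, one disease assessment at Week 6 and another one at Week 12". Patients who, before the Week-12 evaluation, progress, deteriorate clinically or symptomatically from the disease, die of it, stop for unmanageable toxicity, or die or stop because of a treatment-related AE are evaluable non-responders. Starting another antitumor therapy is not on that list.

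**Replacement.** Protocol 6.3.4 and SAP 4 replace patients who "do not have the disease assessment at Week 12", apart from the failure categories above. Patients who refuse treatment before Week 12 for reasons other than related AEs are also replaced.

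**PFS.** SAP 6.1 defines it as the "time from the first day of study treatment to the day of assessment of progression, death or last tumor evaluation". For the all-treated sensitivity analysis, SAP 6.2.2 adds: "Event will be defined as progression or death irrespective of the subsequent therapies received for this analysis".

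**The concern.** Protocol 6.3.2 allows treatment to stop for intercurrent serious illness or by investigator's decision, and SAP Table 10.2.1 has a row for AEs unrelated to treatment. None of these is a PFS3 failure. Protocol 5.5.3 bars other antineoplastic drugs only as concomitant treatment, so it does not cover a switch after PM060184 has stopped.

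Take a patient who stops for one of these reasons after a clean Week-6 scan, begins another drug in Week 8 and has a clean Week-12 scan. Every written condition for success is met, although another drug was being given for part of the interval. If no Week-12 scan is done, the patient is replaced.

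There is no control arm to absorb this, and activity is declared on a count. Other parts of the protocol do react to new antitumor therapy: the end-of-treatment date (6.2), AE and SAE collection (8.5.1, 8.5.2) and the follow-up QLQ-CIPN20 (7.6). The primary endpoint does not. The only all-treated efficacy analysis in the SAP is for PFS and counts events whatever therapy follows, so no planned analysis would isolate the effect.

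**Working it through.** **Inputs (Protocol 9.3).** The null is that "30% or less patients are alive and free of progression at twelve weeks (PFS3"; the alternative is that "50% or more patients are alive and free of progression at 12 weeks". The type I error "associated with this one-sided test is 0.025 and the type II error (beta) is 0.1; hence, statistical power is 90" percent. The final rule is at least 25 of 60; the first-stage rule is at least 7 of 24.

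**The plan's own figure.** With null variance in the test and alternative variance for power:

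n = [1.960·√(0.30·0.70) + 1.282·√(0.50·0.50)]² / (0.50 − 0.30)² = 59.2, rounded up to 60.

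The critical count is 60·(0.30 + 1.960·√(0.21/60)) = 24.96, so 25. Both stated figures reproduce. The exact probabilities are P(X ≥ 25 | 60, 0.30) = 3.62% and P(X ≥ 25 | 60, 0.50) = 92.2%. Applying the first-stage rule gives 3.55% and 91.8%. The comparison below starts from 3.6%. Its excess over the nominal 2.5% is a separate matter.

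**Credited successes.** The documents give no switching rate, so k = 1 to 4 of 60 is an assumption. In each case k patients are certain successes, and the chance is P(X ≥ 25 − k | 60 − k, r), where r is the success rate among the rest. The first-stage rule is ignored here.

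- Case A (worst case): r = 0.30, and the k patients come on top.
- Case B: the k patients were progression-free at Week 6. Under a constant hazard with 30% progression-free at Week 12, their chance of success without a new drug is √0.30 = 0.548. Holding the overall no-switch rate at 30% gives r = (18 − 0.548k)/(60 − k).
- Case C: as B, but the new drug gives each of the k patients a 70% chance of success instead of certainty.

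| k | A | r in B and C | B | C |
|---|---|---|---|---|
| 0 | 3.6% | 0.300 | 3.6% | 3.6% |
| 1 | 5.2% | 0.296 | 4.5% | 3.9% |
| 2 | 7.4% | 0.291 | 5.6% | 4.2% |
| 3 | 10.3% | 0.287 | 6.9% | 4.5% |
| 4 | 14.1% | 0.282 | 8.4% | 4.8% |

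**Replacement.** Assume 5% of enrolled patients switch, are not scanned and are replaced.

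- If all would have failed, the evaluable rate is 0.30/0.95 = 0.316 and the chance of reaching 25 of 60 is 6.4%.
- If they were clean at Week 6 with a 0.548 chance of success, the rate is (0.30 − 0.05·0.548)/0.95 = 0.287 and the chance is 2.1%.

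The sign of the replacement bias therefore depends on who is replaced.

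**The case against.** **The affected group is narrow.** The natural reasons for changing drug (progression, clinical or symptomatic deterioration, toxicity, a related AE) already make the patient a failure, whatever is given next and whatever a later scan shows. Refusers are replaced even with a clean scan. This stands. A reader might infer that starting a new therapy can never lead to a PFS3 failure; Protocol 8.1 and SAP 4 rule that out.

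**A missing scan is not always replaced.** The failure categories are exempt from replacement, and SAP 11.3.1 scores evaluable patients without 12 weeks of follow-up as PFS3 = No. This is correct, but the SAP rule applies only to patients already evaluable. A switcher outside the failure categories with no Week-12 scan is not, so replacement applies.

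**Counting progression regardless of later therapy is a recognised approach.** It also fits the instruction to scan patients who are off treatment. In principle this stands, but the plan does not state it as its choice and does not apply it consistently: related-AE stops are failures and refusers are replaced whatever the scan shows. In a single-arm test of one drug's activity, it also counts the other drug's effect.

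**Main PFS and DOR.** A reader might infer that the main analyses run through subsequent therapy exactly as the sensitivity analysis does. The documents do not establish this. The main rule is unstated, the sensitivity wording hints at a different one, SAP Listing 11.3.2 has a column for the censoring reason, and SAP 8.16 sends data conventions to a separate document. Censoring at new therapy is itself debatable, because it may be informative.

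**Conclusion.** The gap is real but limited. For patients who stop PM060184 before Week 12 for reasons outside the failure and refusal categories, the written rules can turn a switch to another drug into a PFS3 success, or into a replacement if the Week-12 scan is missing. With 25 of 60 as the threshold, a handful of such patients matters: 1 to 4 credited successes move the false-positive chance from 3.6% to 5.2–14.1% at worst, or to about 4.5–8.4% when the patients were already clean at Week 6.

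The number of switchers is assumed throughout and is probably small. The lower range also rests on a constant hazard, and both ranges treat each credited success as certain. Crediting switchers favours PM060184 to the extent that the new drug improves their Week-12 status. Replacing them may bias the result either way. For PFS and DOR, the finding is only that the main-analysis rule is not written in these documents.

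**What to change.** **PFS3.** In Protocol 8.1 and 6.3.4 and SAP 4 and 11.3.1, state that starting any non-protocol antitumor therapy before the Week-12 assessment makes the patient evaluable, PFS3 = No and not replaceable. Report a sensitivity count that ignores new therapy, so that the effect of the rule is visible. Write the rule before outcomes are known.

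**PFS and DOR (clarification only).** State in SAP 6.1 and 6.2.2 which rule the main analysis uses for subsequent therapy, so that a reader can tell how the sensitivity analysis differs from it.

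**Cost.** No new data are needed: subsequent therapy is collected (Schedule footnote 2), summarised (SAP 8.5, Table 12.6.4) and listed (SAP Appendix II). The sample size and threshold do not change. The PFS3 rate may be slightly lower. If the planned 50% had already included one such success per 60 on average, two-stage power would fall from 91.8% to 87.2% (success rate 0.50 − 1/60 = 0.483).
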